## 10. STATISTICAL CONSIDERATIONS

### 10.1 Study Endpoints, Subsets, and Covariates

#### 10.1.1 Primary Endpoint

Percent change in fasting TG level from Baseline at the primary analysis time point.

#### 10.1.2 Secondary Endpoints

- Absolute and percentage change in ANGPTL3 protein, TC, LDL-C, HDL-C, VLDL-C, Non-HDL-C, ApoB (ApoB-48, ApoB-100), ApoCIII, ApoAI, FFA, Lp(a)
- Absolute change in fasting plasma glucose, HbA1c, fasting insulin HOMA-IR, fructosamine and glycated albumin
- Absolute and percent change in weight, SBP and DBP
- Absolute and percent change in hepatic fat fraction (HFF) by MRI-PDFF
- Proportion of subjects reaching hepatic fat fraction (HFF)  $\leq 8\%$  by MRI-PDFF
- Absolute change in Fatty Liver Index (FLI)
- Absolute change in ALT and AST

Evaluate the beneficial effect of ISIS 703802 on changes from Baseline at the primary analysis time point on:

- Adipokines and related metabolic markers such as leptin, adiponectin, phospholipids (e.g. ceramides, sphingolipids, diacylglycerol)
- Body composition as measured by single slice MRI of subcutaneous adipose tissue (SAT) and visceral adipose tissue (VAT), waist circumference, WHR (waist-to-hip ratio), and BMI

[REDACTED]

## 10.2 Sample Size Considerations

Subjects in the placebo arm will be pooled for the statistical analysis in order to compare active and control arms. Therefore, each of the 4 arms will have 24 patients. Considering 10% dropouts, 21 patients per group are expected to complete the study.

A sample size of 21 patients per arm will be able to detect:

- A treatment difference in mean triglycerides of 50% based on a between-patient standard deviation of 46% (Jani et al. 2014) and a two-sample t-test with an unadjusted alpha level of 0.05 with 93% power.
- A treatment difference in mean liver fat of 4.75% based on a between-patient standard deviation of 3.96% (Tiikkainen et al. 2004) and a two-sample t-test with an unadjusted alpha level of 0.05 with 96% power.

A total of approximately 96 subjects (32 subjects per cohort, including 24 subjects per cohort treated with ISIS 703802) will be randomized to ensure that the efficacy of ISIS 703802 will be adequately characterized in the study.

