Statistical Considerations	
The primary efficacy analysis for the primary endpoint will be the pairwise comparison of percent change from Baseline to the primary analysis time point in fasting TG between ISIS 703802 treated groups and placebo group in the Full Analysis Set.
 
The data will be analyzed using an ANCOVA model with the Baseline TG level as a covariate.
 
Dose selection for the further development will be based on the following efficacy and safety considerations; more than 1 dose may meet these criteria. An effective dose, or dose regimen, will be one that achieves a clinically-meaningful reduction in plasma TG levels. Safety will be evaluated on the basis of incidence of expected and unexpected treatment-related SAEs, and other specific safety considerations including the incidence of platelet reductions.
 
Sample Size Considerations:
 
Subjects in the placebo arm will be pooled for the statistical analysis in order to compare active and control arms. Therefore, each of the 4 arms will have 24 patients. Considering 10% dropouts, 21 patients per group are expected to complete the study.
 
A sample size of 21 patients per arm will be able to detect:
 

• A treatment difference in mean triglycerides of 50% based on a between-patient standard deviation of 46% (Jani et al. 2014) and a two-sample t-test with an unadjusted alpha level of 0.05 with 93% power.

• A treatment difference in mean liver fat of 4.75% based on a between-patient standard deviation of 3.96% (Tiikkainen et al. 2004) and a two-sample t-test with an unadjusted alpha level of 0.05 with 96% power.

Sponsor/Collaborator	Akcea Therapeutics, Inc./Ionis Pharmaceuticals, Inc.

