#### **2.3.4 Clinical Experience**

Detailed information concerning the clinical studies conducted with ISIS 703802 can be found in the Investigator's Brochure. A summary is included below.

The Study Drug, ISIS 703802, is being evaluated in Phase 1 in the clinical setting with single doses up to 120 mg and multiple doses up to 60 mg (once per week for 6 weeks). The parent drug ISIS 563580, an unconjugated 2'-MOE modified ASO that has the same base sequence as ISIS 703802, was also evaluated in a blinded, placebo-controlled Phase 1 study.

An interim analysis of ISIS 703802 Phase 1 SAD/MAD Study (ISIS 703802-CS1) was performed in 44 subjects administered single ascending (20, 40 and 80 mg) or multiple ascending doses (10, 20, 40 and 60 mg/week for 6 weeks). Twelve participants were randomly assigned to single-dose groups (9 to active-agent dose groups and 3 to the placebo group) and 32 were randomly assigned to multiple-dose groups (24 to active-agent dose groups and 8 to the placebo group). The main endpoints of the study were safety, tolerability, pharmacokinetics, pharmacodynamics and changes in lipids and lipoproteins. After 6 weeks of treatment, persons in the multiple dose groups treated with ISIS 703802 had dose-dependent reductions in levels of ANGPTL3 protein (reductions of 46.6 to 84.5% from Baseline,  $P < 0.01$  for all doses vs. placebo 1.6%) and in levels of triglycerides (reductions of 33.2 to 63.1% vs placebo 11.4%), LDL cholesterol (1.3 to 32.9% vs placebo 13.6%), very-low-density lipoprotein cholesterol (27.9 to 60.0% vs placebo 4.0%), non-high-density lipoprotein cholesterol (10.0 to 36.6% vs placebo 9.1%), apolipoprotein B (3.4 to 25.7% vs placebo 11.0%), and apolipoprotein C-III (18.9 to 58.8% vs placebo 3.1%). There were no serious adverse events documented during the trial. No protocol-defined injection-site reactions were reported. Of those participants who received the multiple-dose regimen, three reported headache (one who received placebo and two who

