#### **2.4 Rationale for Dose and Schedule of Administration**

The Phase 1 program evaluated ISIS 703802 doses of 10 mg, 20 mg, 40 mg and 60 mg given weekly for 6 weeks that were found to be generally well-tolerated and to induce clinically-relevant reductions in lipid biomarkers. The range of dosing proposed for the present study will provide the equivalent drug exposure of 10 mg (from 40 mg monthly), and 20 mg (from 20 mg weekly and 80 mg monthly) administered weekly, and is predicted (based on modelling of PK/PD data obtained in Phase 1 study) to result in mean reductions from Baseline in TGs ranging from approximately 45 to 55% at steady-state.

Safety data from the available chronic mouse (26-week) and monkey (39-week) studies support once-weekly dosing for chronic administration. The No Adverse Effect Level (NOAEL) for ISIS 703802 in chronic monkey study was determined to be 12 mg/kg/wk.

Preclinical pharmacology experiments in Tg-mice and non-human primates demonstrated that ISIS 703802 achieved an equivalent reduction in ANGPTL3 plasma concentration to that of the unconjugated form, at 1/10th of the unconjugated ASO (ISIS 563580) dose.

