### **2.5.3 Overall Assessment of Benefit: Risk**

ISIS 703802 has demonstrated the ability to reduce ANGPTL3, APOCIII, and TGs by greater than 60% in the Phase 1 study in healthy volunteers. The objective of this study is to assess the effect of TG lowering in these subjects. This study will also investigate the potential of ISIS 703802 in improving the insulin resistance and glucose profile, and decreasing liver and visceral fat content in subjects with high TG levels and T2DM. Although the subjects enrolled in this study will not derive long term benefits due to the short duration of the study, they may derive some short term benefit from improved metabolic health and dietary counselling. The information obtained in the course of this study is critical to further development of ISIS 703802 for hypertriglyceridemia, dyslipidemia, NAFLD and associated metabolic complications and cardiovascular disease.

The protocol identifies that potential risks associated with ISIS 703802 treatment will be mitigated by routine monitoring. Thus, exposure of subjects in this study is justified by the anticipated benefits that may be afforded to the wider population of patients by continued development of ISIS 703802 (see [Section 8.5 Safety Monitoring Rules](#)).

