3.3.1.2 Primary Efficacy Analysis

The percent change from baseline in triglycerides will be analyzed using an ANCOVA model with treatment group as a fixed factor and log-transformed baseline triglycerides as a covariate. The ANCOVA model will use $\log(Y/\text{base})$ as dependent variable, where Y is the post-baseline value of triglycerides and base is the baseline value of the triglyceride. The model will provide an estimate of the log ratio, which will then be converted back to the original ratio scale. The percent change from baseline will then be estimated based on the estimated ratio. Patients with missing primary endpoint will have their fasting triglyceride value imputed using the following multiple imputation method described below.

Missing data for the primary efficacy endpoint will be handled by a multiple imputation model that contains the following variables: log-transformed baseline fasting triglyceride value, log-transformed fasting post-baseline triglyceride values, stratified by treatment (Schafer 1997; Schafer 1999). Imputation of missing data will be conducted under a working assumption of missing at random (MAR), meaning that the propensity for a data point to be missing is not related to the missing data, but it is related to some of the observed data.

The imputations will be performed for post-baseline visits. The Markov Chain Monte Carlo (MCMC) method will be used under the multivariate normality assumption to impute the missing primary endpoint by treatment group (ISIS 703802 treatment group or pooled placebo treatment group). In order to be compliant with the normality assumption, baseline and post-baseline triglyceride data will be log-transformed prior to the imputation process. Jeffreys' prior will be used to derive the posterior distribution of the parameters. The MCMC method will impute 100 datasets in order to estimate the treatment effect.

The primary endpoint will be compared between each ISIS 703802 treatment group and the pooled placebo group for each of the 100 imputed datasets. The estimates from the 100 fitted models will be combined to provide an overall estimate, with corresponding CIs and p-value ([Little and Rubin, 2002](#)). Results from the ANCOVA model will be tabulated by ISIS 703802 treatment groups compared to the pooled placebo group.

For fasting triglycerides, all observed values, change from baseline and percentage of change will be summarized by analysis visit using descriptive statistics in FAS.

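### Does the 93% power statement need correcting because the 50-point triglyceride difference has no stated placebo change and the primary test is on the log-ratio scale?

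*Protocol*

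**What the plan says.** Protocol 10.2 states the detectable effect as "A treatment difference in mean triglycerides of 50% based on a between-patient standard deviation of 46" percent, using "a two-sample t-test with an unadjusted alpha level of 0.05 with 93% power". It assumes 24 patients in each of four groups (three active, one pooled placebo) and 10% dropout, leaving 21 per group. The synopsis and SAP 3.2.5 carry the same figures. The literature citation is attached to the SD; none is attached to the 50.

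Protocol 2.4 gives the only effect prediction for these doses, from Phase 1 PK/PD modelling: "mean reductions from Baseline in TGs ranging from approximately 45 to 55% at steady-state". Protocol 2.3.4 reports, after six weeks in the Phase 1 multiple-dose groups, "levels of triglycerides (reductions of 33.2 to 63.1% vs placebo 11.4" percent, with 8 subjects on placebo.

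Protocol 10.6.3.1 analyses percent change from Baseline by ANCOVA with Baseline triglycerides as covariate. SAP 3.3.1.2 refines this to an "ANCOVA model with treatment group as a fixed factor and log-transformed baseline triglycerides as a covariate", with the log of the post-baseline to baseline ratio as the dependent variable and multiple imputation of missing values in the Full Analysis Set.

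On use of the results, the synopsis says "An effective dose, or dose regimen, will be one that achieves a clinically-meaningful reduction in plasma TG levels", alongside safety considerations.

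**The concern.** Two features make the 93% look unreliable.

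First, the primary comparison is with pooled placebo, but the only prediction near 50 is a change from Baseline. The two are equal only if placebo stays flat. Placebo fell by 11.4% in Phase 1, and Protocol 2.5.3 says of participants that "they may derive some short term benefit from improved metabolic health and dietary counselling". If placebo falls here too, the true difference is below 50. The 40 mg every-4-weeks arm, with the lowest exposure, would be the most exposed to this.

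Second, the power calculation uses percentage points, while the SAP's primary test uses log ratios with a baseline covariate. No log-scale SD is given, so the power of the planned test cannot be derived.

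Amendment 3 set the sample size at 96 on the ground that the study stays adequately powered. If that rested on an optimistic difference, the lowest-dose comparison could be weaker than a reader would suppose.

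**Working it through.** **Inputs.** Difference 50 points, SD 46 points, 21 per arm, alpha 0.05 (Protocol 10.2); two-sided testing (Protocol 10.6). Predicted reductions 45 to 55% (Protocol 2.4); Phase 1 placebo fall 11.4% (Protocol 2.3.4). The 50% is read as percentage points of percent change, since the SD is in the same unit.

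**1. The plan's own figure.** The standard error of a difference is 46 × √(2/21) = 46 × 0.3086 = 14.20 points. The non-centrality parameter is 50/14.20 = 3.52 on 40 degrees of freedom. Exact non-central t power is 93.0%, so the stated figure reproduces.

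**2. Sensitivity to the placebo change.** Same SD, unadjusted t-test. The column with 24 per arm is an upper bound on what imputing dropouts could recover.

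| Active reduction | Placebo fall | Difference | Power, 21 per arm | Power, 24 per arm |
|---|---|---|---|---|
| 55 | 0 | 55 | 96.6% | 98.2% |
| 50 | 0 | 50 | 93.0% | 95.8% |
| 45 | 0 | 45 | 87.1% | 91.3% |
| 55 | 11.4 | 43.6 | 85.0% | 89.5% |
| 45 | 5 (assumed) | 40 | 78.5% | 83.9% |
| 50 | 11.4 | 38.6 | 75.6% | 81.2% |
| 45 | 11.4 | 33.6 | 63.7% | 69.7% |

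With 21 per arm, 80% power needs 40.8 points. An arm at 45% therefore stays at or above 80% if placebo falls by no more than 45 − 40.8 = 4.2 points.

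Baseline adjustment is not in the table. An assumed correlation of 0.3 between baseline and outcome reduces the SD to 46 × √(1 − 0.09) = 43.9 and raises the 40-point case with 21 per arm from 78.5% to 82.2%.

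**3. Log-ratio scale.** The same formula is used with the log of the active-to-placebo ratio as the difference and a log SD in place of 46. Reductions are treated as geometric. The documents give no log SD, so a range is assumed.

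| Reduction relative to placebo | Log difference | SD 0.44 | 0.50 | 0.60 | 0.70 |
|---|---|---|---|---|---|
| 50% | 0.693 | 99.9% | 99.2% | 95.5% | 87.9% |
| 45% | 0.598 | 99.0% | 96.6% | 88.3% | 77.1% |
| 38% (0.55/0.886) | 0.477 | 92.9% | 85.4% | 71.0% | 57.7% |

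For a halving, 93% corresponds to a log SD of 0.64. The stated power is conservative below that value and optimistic above it.

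**4. Expected precision.** The 95% interval half-width for each comparison with placebo is 2.021 × 14.20 = 28.7 points (21 per arm, unadjusted).

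**The case for a change.** The best case for an edit is that it costs a sentence or two and would make the claim of adequate power readable. The sample-size text should say whether the 50 is a difference from placebo or a change from Baseline, because power runs from 64% to 97% across the protocol's own predicted range, depending on the placebo change. Because dose selection rests on the size of the effect, the half-width of about 29 points would tell a reader more than a power figure.

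Some of this stands. The sample-size sections do not link the 50 to Protocol 2.4, state no placebo change, and give no log-scale SD or expected precision. That the 50 came from the 45 to 55% prediction is a reasonable inference, but the documents do not say so.

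The rest is weaker. Protocol 10.2 says what 21 per arm can detect; it does not forecast 50 points in every arm. The 63.7% combines the low end of the prediction, the full placebo fall seen in 8 Phase 1 subjects over six weeks, completers only, and no covariate. The Phase 1 study was in healthy volunteers (Protocol 2.5.3). Here, diet is stable or stabilised for four weeks (Protocol 3.1), background lipid medication is stable (Protocol 5.1), and baseline triglycerides average two measurements (Protocol 10.4). These features do not guarantee a flat placebo arm, but they tend to limit placebo change. The dietary counselling remark says nothing specific about triglycerides on placebo.

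On scale, Protocol 10.6.3.1 describes percent change, as the power statement does; the log ratio enters with the SAP. A t-test is a common planning stand-in for ANCOVA, and the log-scale calculation points in neither direction without an SD the documents lack.

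**Conclusion.** No change is needed. The 93% is correct for its stated inputs, and no figure in the sample-size sections is wrong. What is missing is explanation: the source of the 50, the placebo change behind it, and how the t-test relates to the SAP's log-ratio model.

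The possible overstatement of power has a definable size only under added assumptions. At SD 46 and 21 per arm, an arm at a 45% reduction has 87.1% power with a flat placebo, 78.5% with an assumed 5-point fall, and 63.7% if the Phase 1 fall recurs in full. Placing the 40 mg arm at 45% is an inference from its exposure, since Protocol 2.4 gives a range and no per-arm values. For the planned log-ratio test, the documents do not settle whether 93% is high or low.

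None of this carries into the results. The planned number is 96 either way, and neither the 50 nor the 93% enters the primary model, the imputation or the tests. Dose selection depends on a clinically meaningful triglyceride reduction and on safety, and the intervals reported will reflect the variability actually observed. An analyst following the plan as written reaches the same estimates and conclusions with or without the extra sentences.

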## 10.3 Populations

**Full Analysis Set (FAS):** All subjects who are randomized, received at least 1 dose of Study Drug (ISIS 703802 or placebo), and have a Baseline TG assessment. The FAS represents the practically-feasible intent-to-treat (ITT) population as delineated in ICH Guideline E9. This population will be used for the primary analysis of efficacy.

**Per Protocol Set (PPS):** Subset of the FAS who received within 6 months at least 25 weekly doses of Study Drug for subjects randomized to Cohorts A, and at least 5 monthly doses of Study Drug for subjects randomized to Cohorts B and C, and who have no major protocol violations that could compromise the interpretation of efficacy. Major violations will be determined prior to unblinding for statistical analysis. This population will be used for supportive inferences concerning efficacy.

**Safety Set:** All subjects who are randomized and receive at least 1 dose of Study Drug. This population will be used for all safety analyses.

**PK Population:** All subjects who are randomized and received at least 1 dose of ISIS 703802, and have at least 1 evaluable concentration result post first dose. This population will be used for analysis of PK data.

## 10.4 Definition of Baseline

Baseline for TG, ANGPTL3, TC, LDL-C, HDL-C, VLDL-C, Non-HDL-C, ApoB (ApoB-48, ApoB-100), ApoCIII, ApoAI, FFA, Lp(a), and other lipid measurements will be defined as the average of Day 1 pre-dose assessment and the last measurement prior to Day 1 pre-dose assessment. The Baseline for other measurements is defined as the last non-missing assessment prior to the first dose of Study Drug.

## 10.5 Interim Analysis

No interim efficacy analysis is planned.

## **10.6 Planned Methods of Analysis**

Summary tabulations will be provided for disposition, demographic, Baseline, efficacy, and safety data as noted in the following sections. Hypothesis testing will be used for the primary efficacy endpoint and select secondary efficacy endpoints.

All eCRF data, lab data transfers, and any outcomes derived from the data will be provided in the subject data listings. Subject data listings will be presented for all subjects enrolled into the study. Descriptive summary statistics including n, mean, median, standard deviation, standard error, interquartile range (25th percentile, 75th percentile), and range (minimum, maximum) for continuous variables, and counts and percentages for categorical variables will be used to summarize most data. Where appropriate, p-values will be reported. All statistical tests will be conducted using 2-sided tests with 5% Type I error rate unless otherwise stated.

### ***10.6.1 Demographic and Baseline Characteristics***

Demographic and Baseline characteristics will be summarized using descriptive statistics by treatment group. The subject disposition will be summarized by treatment group. All subjects enrolled will be included in a summary of subject disposition.

### ***10.6.2 Safety Analysis***

#### ***10.6.2.1 Adverse Events***

Treatment duration and amount of Study Drug (ISIS 703802 or placebo) received will be summarized by treatment group. Subject incidence rates of all AEs will be tabulated by MedDRA system organ class, and by MedDRA preferred term. Narratives of treatment-emergent deaths, serious and significant AEs, including early withdrawals due to AEs, will also be provided.

All treatment-emergent AEs, all treatment-emergent AEs potentially related to Study Drug, all treatment-emergent serious AEs, and all treatment-emergent serious AEs potentially related to Study Drug (ISIS 703802 or placebo) will be summarized.

#### ***10.6.2.2 Clinical Laboratory Data***

Laboratory tests to ensure subject safety including chemistry panel, complete blood count (CBC) with differential, coagulation panel, complement, etc., will be summarized by study visits for each treatment group. These safety variables will also be presented as change and percent change from Baseline over time after Study Drug (ISIS 703802 or placebo) administration, as appropriate. In addition, the number of subjects who experience abnormalities in clinical laboratory evaluations will be summarized by treatment group.

#### ***10.6.2.3 Vital Signs and Examinations***

Vital sign and ECG measures will be tabulated by treatment group.

### **10.6.3 Efficacy Analysis**

#### **10.6.3.1 Analysis of Primary Efficacy Endpoint**

The primary analysis of the primary endpoint will be the pairwise comparison of percent change from Baseline to primary analysis time point in TG between ISIS 703802 treatment groups and pooled placebo group in the FAS. The data will be analyzed using an analysis of covariance (ANCOVA) model with the Baseline TG as a covariate. Missing data may be handled by LOCF or multiple imputation methods ([Schafer 1997](#); [Shaffer 1999](#)).

The primary efficacy analysis will take place after the last subject has completed the primary analysis time point, and the database has been locked.

The following sensitivity analyses will be conducted:

- The primary analysis will be repeated in the PPS
- The primary efficacy endpoint will be analyzed using a Wilcoxon Rank Sum test on both FAS and PPS, and the treatment effect will be estimated using Hodges-Lehmann estimator

Additional sensitivity analyses may be conducted as appropriate; the details of these analyses will be outlined in the SAP.

